endorsed a four or higher on the BSSS and met inclusion criteria, they were offered participation in the study. Interested patients also had clearance from their primary counselors to confirm they did not meet exclusion criteria. Eligible individuals were provided with a written and oral informed consent. The PI or RA reviewed the informed consent and answer any questions or concerns that individuals had about study procedures, confidentiality, data analysis, and dissemination of results. Once written informed consent was obtained, participants were notified of the group start date within one week of signing the consent form. Participants were asked to complete a battery of paper-and-pencil assessments within one week prior to the start of the first session. After assessments were completed, cohorts of participants were randomized to receive either Standard MBRP or TI-MBRP. A non-interventionist RA used computer randomization software to assign to cohorts to either Standard MBRP or TI-MBRP. Ten TI-MBRP and Standard MBRP groups were implemented simultaneously at five sites for maximization of participants within the given timeframe over a 12-month period.

After the first Standard MBRP and TI-MBRP session, participants were provided with a CD player and CD with audio-recordings of guided meditation practices used in the intervention (i.e., body scan, breath awareness) to use daily as a part of their homework requirements. Cohorts randomized to the TI-MBRP group were given an additional CD with mindfulness practices administered only in the TI-MBRP course.

Participants completed a post-course assessment battery within one week of the completion of the eight-session course, taking place over four weeks. They had access to doctoral level psychology graduate students and to their primary counselor to discuss any distressing feelings related to the study.

One week after post-course assessments, participants were invited to participate in a focus group to discuss what was helpful about the intervention and what could be changed. Focus groups were audio-recorded, transcribed, and analyzed in NVivo Pro V12. Frequently discussed topics within focus groups were used to inform changes to the pilot protocol which will optimize interventions within TI-MBRP targeting craving, substance use and PTSD symptoms.

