Feasibility and acceptability was assessed using multiple metrics. Based on completion rates of an RCT conducted at the Phase I clinical site (Witkiewitz et al., 2014), we assessed recruitment and retention rates, with a target rate retention of 60% or better. Participant overall course satisfaction was measured by the OCSS. Treatment dropout was monitored by tracking attendance at each session and information will be gathered from clinical sites to determine whether the participant dropped out of treatment altogether or the study. This will allow assessment of any systematic bias or characteristics of TI-MBRP drop-outs vs. course completers.

To assess initial efficacy, Repeated Measures Analysis of Variance (RM ANOVA) was used to examine differences between TI-MBRP and Standard MBRP in substance use, craving, and PTSD symptoms over time. When an interaction effect was detected, an ANCOVA was used

to determine the timepoint in which two conditions differed, controlling for baseline scores (Fields, 1999). Mediators and moderators were examined using PROCESS in SPSS 26.0 to help identify factors that explain or support change in the relationships between PTSD symptom severity and craving, and PTSD symptom severity and substance use.

For Phase II qualitative data collection and analyses, ten one-hour long focus groups were audio recorded once participants completed either TI-MBRP or Standard MBRP. Women were asked eight questions to assist with the refinement of the pilot protocol (See Appendix .

Questions were as follows:

1. What was your overall experience like in this group?
2. How did this class help with understanding the relationship between substance use and trauma?
3. How did this class help with processing the impact of traumatic events on aspects of your life now?
4. How was this group different or similar from other substance use and trauma groups you have completed in the past?
5. Is there anything that you felt was missing from this program that would have enhanced your experience while taking this course?
6. What aspects of the treatment did you find helpful and/or important in your recovery process?
7. What aspects did you dislike and feel could be changed or taken out?
8. Would you recommend this group to other women who have not taken it yet?
9. How would you describe the group to other women who have not taken this group yet?

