10. Are there certain people you would not recommend this group to or think that this group would be inappropriate for?

All audio recordings were transcribed by a third party company, TranscribeMe. Transcribed focus-group data were uploaded into NVivo 12 Pro and coded by the PI and two RAs.. A constant comparison analysis (Fram, 2013; Leech & Onwuegbuzie, 2011) was implemented to code relevant information pertinent to refining the pilot protocol of TI-MBRP, which is recommended for pilot qualitative research (Leech & Onwuegbuzie, 2007). Three coders went through several iterations of extracting themes from transcribed audio recordings on what

women thought the most and least helpful aspects of the program were.

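### The two focus-group questions on the class's effect on trauma understanding and processing presuppose benefit, and no listed question asks directly about worsening; the weakness is confined to the qualitative evidence

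*Combined protocol and SAP*

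**What the plan says.** The focus groups are described in two places in the combined protocol and SAP, both within Phase II.

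- **Procedures.** One week after the post-course assessments, women were invited to discuss what had helped and what might be changed. On use of the material: "Frequently discussed topics within focus groups were used to inform changes to the pilot protocol".
- **Design and analyses.** Ten one-hour groups were held after women had completed either course. The purpose and number of questions are given as "Women were asked eight questions to assist with the refinement of the pilot protocol", but ten questions follow. Question 2 is "How did this class help with understanding the relationship between substance use and trauma" and question 3 is "How did this class help with processing the impact of traumatic events on aspects of your life now". Criticism is invited by question 5 ("Is there anything that you felt was missing from this program that would have enhanced your experience while taking this course"), question 7 ("What aspects did you dislike and feel could be changed or taken out") and question 10 ("Are there certain people you would not recommend this group to or think that this group would be inappropriate for"). Three coders then drew out themes on what women found most and least helpful.

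The opening of Design and analyses lists safety with feasibility and acceptability as what this first study explores. The description of TI-MBRP in Phase I presents trauma education and trauma processing as what is added to standard MBRP.

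**The concern.** A question that asks how a class helped leaves a woman whom it did not help, or whom it upset, to reject the premise in front of her group. Agreement with such a question is hard to tell from real benefit. Here the wording falls on the content that distinguishes the new intervention.

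Three features of the plan add to this.

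- The Personnel section gives the post-intervention focus groups to the principal investigator and three research assistants, and says that the principal investigator and research assistants delivered the courses. The principal investigator also made the Phase I protocol revisions and was one of the coders. The document does not say whether a group was questioned by the person who had taught it, but it does not exclude it.
- The ten groups cover both arms and only one question list is given. Women in standard MBRP were therefore apparently also asked how their class helped them process trauma, so agreement in either arm is hard to interpret.
- The focus groups feed the revision of the manual, and frequency of discussion is the only selection rule stated. Worsening in a few women is the kind of information that such a rule can pass over.

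At stake is whether the revised manual carried into the larger trial reflects uncommon bad experiences of the trauma content as well as common good ones.

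**Working it through.** No formula applies, because the point concerns wording. The check was to classify the ten listed questions and then see what else in the plan could supply the missing information.

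| Type of question | Questions | Count |
|---|---|---|
| Presupposes that the class helped | 2, 3 | 2 |
| Asks for helpful aspects, without a stem asking how it helped | 6 | 1 |
| Invites criticism or limits | 5, 7, 10 | 3 |
| Neutral | 1, 4, 8, 9 | 4 |
| Asks directly about worsening | none | 0 |

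The total is 2 + 1 + 3 + 4 = 10. Benefit-framed items (2, 3, 6) and critical items (5, 7, 10) are therefore 3 to 3.

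**Sensitivity to the stated count.** The text says eight questions. If only the first eight were asked, the split is 3 benefit-framed (2, 3, 6), 2 critical (5, 7) and 3 neutral (1, 4, 8), and question 10 was never put.

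**Where the leading items fall.** Question 4 mentions trauma groups, but only to compare this group with others. Questions 2 and 3 alone ask what the class did for a woman's understanding or processing of trauma. Both are leading.

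**Whether the critical items cover worsening.** Something missing (question 5) or disliked (question 7) is not the same as something that made a woman worse. Question 10 comes nearest, but it asks about other people. A woman could volunteer worsening under questions 1, 7 or 10; nothing asks her to.

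**What else in the plan bears on worsening.**

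- Substance use, craving and PTSD symptoms are compared between arms over time by repeated measures ANOVA, from self-report at baseline, post-course and follow-up. This compares condition means; it does not identify which content upset a particular woman.
- Research assistants were trained in adverse-event protocols (Personnel), and women had access to graduate students and their primary counselor about distress (Procedures). Neither is described as feeding the revision of the manual.
- Acceptability and feasibility rest on recruitment, retention (target 60% or better), overall satisfaction on the OCSS, and attendance and dropout. The focus groups are not named in that list.

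The gap is therefore specific: a lean in the answers to two questions, and no direct route from an uncommon experience of worsening to the revision step.

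**The case against.** The strongest case on the other side is that the guide as a whole is balanced. It opens with a neutral question, its benefit-framed and critical items are equal in number, and question 7 presupposes dislike, which leads the other way. The coders looked for the least helpful aspects as well as the most helpful. This stands, and it rules out calling the whole guide one-sided. It does not change the wording of questions 2 and 3 or supply a question on worsening.

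A reader might go further and infer that the acceptability evidence as a whole is tilted towards benefit, or that the focus groups are its main source. The documents do not support either. Acceptability is assessed by the several measures listed above, and the stated purpose of the focus-group questions is to refine the pilot protocol. Nor does the wording bias the quantitative PTSD and craving outcomes, which come from separate self-report measures.

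A reader might also try to calculate how many women with a bad experience would go unheard in each group. That cannot be done from the documents. They give no rate of worsening, no focus-group attendance and no threshold for a frequent topic. They say that frequent topics informed changes, not that infrequent ones were discarded, and the coding is described as constant comparison, not counting.

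Two further objections stand in part. The reference to the appendix is incomplete in the available text, so facilitator prompts about worsening cannot be excluded. And the document reports the sessions as already held, so new wording cannot change this study's data.

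**Conclusion.** The point holds in a limited form and is minor. Both questions on the class's effect on trauma understanding and processing are leading, and none of the ten listed questions asks directly about worsening, in a study that names safety among what it explores. As a result, answers to questions 2 and 3 may lean towards benefit, and uncommon reports of worsening may not reach the revision step. The consequence stops at the qualitative evidence.

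This rests on two assumptions: that the listed questions are the guide as used, without further prompts on worsening, and that frequency of discussion was the working rule for choosing changes, as the Procedures section indicates. The size of any lean cannot be estimated.

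**What to change.** **For this study.** Re-read the existing transcripts, code every report of worsening of symptoms, craving or distress, and take each one to the revision step however rarely it is mentioned. State in the report that questions 2 and 3 were leading, and interpret their answers accordingly. Reconcile the stated eight questions with the ten listed, and say whether question 10 was put to every group. If facilitator prompts on worsening were used, report them.

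**Wherever the guide is used again, including the larger trial.** Use neutral stems, for example:

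- Question 2: *What effect, if any, did this class have on how you understand substance use and trauma?*
- Question 3: *What effect, if any, did this class have on how traumatic events affect your life now?*
- One added question, placed early: *Did anything in the class make your symptoms, craving or distress worse?*

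**Cost.** One coding rule, one further pass through transcripts that already exist, a sentence of limitation in the report, and the rewording of two questions plus one addition. The one-hour session and the number of coders need not change. Because the groups were held after course completion, a direct question would still not reach women who left early; the dropout information from the clinical sites has to be read alongside it.
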